### 5.2 Interim Analyses

Not Applicable.

### 5.3 Subgroup Analyses

The endpoints which would be presented using IPSS score as subgroup factor of are (0-7) Mildly symptomatic, (8-19) moderately symptomatic and (20-35) severely symptomatic.

All subgroup analyses are exploratory.

### 5.4 Protocol Deviations

No protocol deviations recorded due to retrospective study design.

### 5.5 Device Deficiencies

Summary table will be generated based on device deficiencies with count and percent for the available parameters. The counts and percentages of serious AEs in connect to the device deficiencies will be presented. A data listing will be also provided by subject, deficiency type, and if it leads to any event and preventive action taken for that.

### 5.6 Justification of Pooling

This is a single site study therefore all the data collected at the site will be included in the analysis.

### 5.7 Multivariable Analyses

No multivariate analysis is included for the primary or other endpoints.

## **5.8 Other Analyses**

Missing data will be excluded for primary analysis in this small sample size study. Based on the missing data during data review, Imputation with mean or median where applicable for continuous variable, and tipping point analysis for categorical variable might be conducted for sensitivity analysis. Incorrect and unreasonable data will be clarified before database lock.

Subject disposition (e.g., number completing the study) will be summarized with frequency tables and percentages.

Non-serious AE's and SAE's will be summarized as the number of events and rate per subject by MedDRA system organ class (SOC) and preferred term.

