**Table 9.1-1: The data collection schedule**

Procedure/Assessment	Baseline/pre-procedure	Index Procedure	Post procedure/Prehospital Discharge	follow-up post-procedure #
Informed consent				X&
Demographics	X			
Medical history	X			
Physical examination (height, weight, etc)	X			X
Prostate volume (MRI, DUS)*	X			X
Uroflowmetry(Qmax, Urinary volume )	X			X
PVR	X			X
IPSS	X			X
QoL	X			X
IIEF	X			X
MSHQ-EjD	X			X
Procedure information		X		
Length of catheterization			X	
Surgical retreatment				X
Medication(s) used(LUTS /BPH)	X		X	X
Device Defect (if available)		X		
Adverse events assessment		X	X	X

Note: # All information of subjects available before the defined end of study will be collected in this retrospectively study, data missing will be allowed.

\*Prostate volume -data form MRI and DUS are collected, MRI data will be preferred to used for statistic, DUS data will be used ONLY MRI data unavailable.

&Only written informed consent form is provided after initiation , data will be collected.

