#### **3.1 Primary Effectiveness Endpoint**

Primary Efficacy Endpoint is IPSS change at 3-6M post Rezūm procedure.

International prostate symptom score (IPSS) is a questionnaire used to indicate the severity of LUTS symptoms, there are 7 questions relating to different symptoms subjects be experiencing and one question relating to overall quality of life.

IPSS scores will be collected at baseline and post procedure. If several IPSS scores are collected between 90 and 182 days, the last IPSS score for 3-6 months post procedure will be used to assess the primary efficacy endpoint.

Reduction in IPSS score from Baseline = IPSS score at baseline - IPSS score at 3-6M post procedure.

The improvement of IPSS score of 30% will be calculated for 3-6 months post procedure against baseline.

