##### **3.1.1 Hypotheses**

$$H_0: \Delta \leq 5.5$$

$$H_1: \Delta > 5.5$$

Where  $\Delta$  = reduction in IPSS score at 3-6 month compared to baseline

The mean reduction in IPSS score at 3-6 month from baseline will be calculated with its 90% confidence interval. If the lower bound of the one-sided 95% CI is greater than 5.5 then the null hypothesis will be rejected, and the primary endpoint will be met.

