##### **3.1.2 Sample Size**

In Rezūm Pivotal II study, IPSS score represents a  $11.2 \pm 7.6$ -point reduction at 3M post Rezūm procedure in treatment arm, while  $4.3 \pm 6.9$ -point reduction in sham control. In Pivotal trial, IPSS score in treatment group decreased 25% (5.375) compared to sham control group is recognized as meaningful. For this retrospective RWS study, a performance goal (PG) of 5.5 was deemed as clinically meaningful, and the expected score reduction is assumed to be 10 at 3-6M post Rezūm procedure.

The sample size is calculated according to below formula:

$$n = \frac{(Z_\alpha + Z_\beta)^2 * \sigma^2}{\delta^2}$$

n is sample size,  $\delta = 4.5$  (since 5.5 is the performance goal and 10 is expected IPSS change),  $\sigma = 7.6$ ,  $\alpha=0.05$ ,  $\beta=0.20$  (power=80%). Considering the small sample size needs to be iterative distribution, 22 subjects will provide more than 85% power. As this is retrospective study, there are chances of missing data in the study. A sample size up to 30 are expected to yield 22 treated subjects with available data at 3-6 months post procedure.

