#### **4.1.1 Efficacy Analysis Set**

The efficacy analysis set includes subjects with IPSS scores at baseline and at 3-6 months post-procedure.

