#### **4.1.2 Safety Analysis Set**

The safety analysis set includes all enrolled subjects who has been treated with Rezūm system in hospitals in Hainan BOAO medical pilot zone.

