### 7.3 Methods for Handling Missing Data

Missing data will be excluded for primary analysis in this small sample size study.

Sensitivity Analysis will be performed by imputing missing values with Last Observation Carried Forward (LOCF) method and Worst-case scenario method using values at baseline where applicable for continuous variable.

When calculating rates of all adverse events, both device and/or procedure related with missing event date (i.e. mm/dd/yyyy), the ideal is to work with safety and/or data management representatives to query sites for missing data. However missing and partial missing dates may be handled as using the worst-case scenario as follows:

Partial Date	Action Taken
Entire adverse event onset date is missing	The procedure date will be used for the onset date.
The month and the day of the month are missing but the year is available	January 1 st will be used for the month and day of the onset date. However, if the imputed date falls before the procedure date, then the procedure date will be used for the onset date.
Day is missing, but the month and year are available	The 1 st will be used as the day of the onset date. However, if the imputed date falls before the procedure date, then the procedure date will be used for the onset date.

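### SAP 5.8 permits single mean or median imputation as an optional sensitivity analysis; if the mean IPSS change is imputed, the standard error is understated and no information is added

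*SAP*

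**What the plan says.** The primary analysis drops subjects with missing data (SAP 5.8 and 7.3). Two sections then describe sensitivity analyses for continuous variables.

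- SAP 5.8, which follows Protocol 10.2.3, is optional and leaves the choice until the missing data have been reviewed: "Imputation with mean or median where applicable for continuous variable, and tipping point analysis for categorical variable might be conducted for sensitivity analysis".
- SAP 7.3 is a commitment: "Sensitivity Analysis will be performed by imputing missing values with Last Observation Carried Forward (LOCF) method and Worst-case scenario method using values at baseline".

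Neither section refers to the other, and neither names IPSS. Since IPSS change is the primary continuous variable, both apply to it.

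Missing values are expected. The note to the data collection schedule says "data missing will be allowed", and SAP 3.1.2 says "A sample size up to 30 are expected to yield 22 treated subjects with available data at 3-6 months post procedure".

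No population is named for the sensitivity analyses. SAP 4.1.1 reads "The efficacy analysis set includes subjects with IPSS scores at baseline and at 3-6 months post-procedure", so for this endpoint that set has nothing to impute. The only other set is wider: "The safety analysis set includes all enrolled subjects who has been treated with" the device (SAP 4.1.2). SAP 3.1 fixes the follow-up window ("If several IPSS scores are collected between 90 and 182 days"), but SAP 7.3 does not say which score is carried into it.

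**The concern.** A sensitivity analysis should show how far the result depends on what is assumed about the missing values. Imputing the mean of the observed changes cannot do that. Each imputed subject sits exactly on the mean, so the estimate does not move, the SD shrinks, and the standard error is divided by the root of a sample size that was not observed. The interval comes out narrower than the complete-case interval, and the result looks firmer with no further data behind it.

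What is at stake is the reported robustness of the IPSS result in a small retrospective study intended to support approval. The same weakness affects any other continuous endpoint handled this way, because SAP 3.1.3 attaches a 95% confidence interval to each mean.

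**Working it through.** **Inputs.** SD 7.6, performance goal 5.5, expected reduction 10, alpha 0.05 and 22 evaluable subjects of up to 30 (SAP 3.1.2). The decision rule is one-sided: "If the lower bound of the one-sided 95% CI is greater than 5.5 then the null hypothesis will be rejected" (SAP 3.1.1). Eight missing is 30 − 22, an inference from the plan's figures; fewer are shown as well.

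**1. The plan's own figure.** One-sample t-test, one-sided 0.05, n = 22: noncentrality 4.5/(7.6/√22) = 4.5/1.620 = 2.78, power 85.1%. The stated power of more than 85% reproduces, so these inputs are the plan's own.

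**2. Complete case.** SE = 7.6/√22 = 1.620. At an observed mean of 10 the lower limit is 10 − 1.721 × 1.620 = 7.21. The smallest mean that passes is 5.5 + 1.721 × 1.620 = 8.29.

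**3. Mean change imputed.** With n observed, m imputed and N = n + m, the SD becomes 7.6 × √((n − 1)/(N − 1)) and the SE is that SD divided by √N. For m = 8: SD = 7.6 × √(21/29) = 6.47; SE = 6.47/√30 = 1.181, a ratio of 0.729 to the complete-case SE. The lower limit is 10 − 1.699 × 1.181 = 7.99, and the smallest passing mean is 5.5 + 1.699 × 1.181 = 7.51.

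**4. Error if this limit were read against 5.5.** With data missing completely at random and a true reduction of 5.5, the imputed analysis passes when the observed t statistic (21 df) exceeds t(0.95, N − 1) × SE ratio. For m = 8 that is 1.699 × 0.729 = 1.238, which has probability 0.115.

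| Imputed (22 observed) | SE | Lower limit at mean 10 | Smallest passing mean | One-sided error |
|---|---|---|---|---|
| 0 | 1.620 | 7.21 | 8.29 | 5.0% |
| 2 | 1.482 | 7.46 | 8.04 | 6.6% |
| 4 | 1.366 | 7.67 | 7.83 | 8.2% |
| 6 | 1.267 | 7.84 | 7.66 | 9.9% |
| 8 | 1.181 | 7.99 | 7.51 | 11.5% |

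**5. Follow-up score imputed instead.** SAP 5.8 does not say whether the change or the 3-6 month score would be filled in. If it is the score, imputed subjects keep their baseline variation. The documents give no baseline SD or correlation; I assumed an SD of 5 to 6.5 and a baseline to follow-up correlation of 0 to 0.3. Simulation with 8 of 30 imputed gives an average SE of about 1.26 to 1.32 and a one-sided error of about 6.5% to 9%. The direction is the same and the effect is smaller.

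**6. Median change imputed.** The spread still shrinks, but the estimate now moves toward the median. With 8 imputed, mean 10 and an assumed median of 7.0: mean (22 × 10 + 8 × 7)/30 = 9.20, SD 6.61, lower limit 7.15. With an assumed median of 9.0: mean 9.73, SD 6.48, lower limit 7.72. Against 7.21 for complete cases, the limit can move either way.

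**The case against.** The strongest reply is that nothing decisive rests on this. The rule in SAP 3.1.1 applies to the primary analysis, which excludes missing data. Mean imputation is optional, is not tied to IPSS by name, and would appear beside the committed SAP 7.3 analyses. This stands. The 11.5% describes how the imputed limit would behave if someone read it against 5.5; it is not the error rate of the trial's test. It also needs the optional method to be run on the change score with 8 missing completely at random.

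Three stronger readings are tempting, and the documents do not support them.

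- A reader might infer that SAP 5.8 and 7.3 contradict each other. One is optional and the other is committed, and both can be run. What is missing is a cross-reference.
- A reader might set the mean-imputed limit (7.99) against a baseline-value limit and take a split around 5.5 as the measure of the defect. With 22 of 30 observed and a mean of 10, imputing a reduction of 0 for the other eight gives 4.89. But the complete-case limit, 7.21, also passes, so the gap remains if mean imputation is deleted. It shows a worst-case analysis doing its job.
- A reader might infer that the committed analyses cannot be run because no population or carry-forward rule is given. Only two analysis sets exist and the efficacy set is complete by definition, so most analysts would use treated subjects with a baseline score. These are details to write down.

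**Conclusion.** The point holds and is minor. Single mean imputation, as SAP 5.8 permits it, gives error bars that are too small and tests nothing about the missing data. With SD 7.6, 22 observed and 8 imputed, the SE is understated by 27% if the change is imputed (1.18 against 1.62), and by less if the follow-up score is imputed. Relative to the complete-case result, imputing the mean change would alter a reading against 5.5 only for observed means between 7.51 and 8.29.

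The size rests on roughly normal changes, the planned SD and an inferred shortfall of 8; with 2 imputed the SE is 1.48. The error rates also assume data missing completely at random. The primary conclusion is not in question.

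**What to change.** Amend the SAP only, before the primary analysis, by the route in SAP 5.9.

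1. In SAP 5.8, remove single mean and median imputation for IPSS and for the other continuous endpoints with a baseline (Qmax, PVR, QoL, IIEF, MSHQ-EjD), and state that SAP 7.3 governs them.
2. For operation time and length of catheterization, which have no baseline, report available cases with the number missing. Do not report a confidence interval computed from mean-imputed data. Keeping the method for these two would repeat the same fault.
3. State that the IPSS sensitivity analyses use all subjects in the safety analysis set with a baseline IPSS.
4. State that last-observation imputation carries the last post-procedure score before day 90, or the baseline score if there is none.

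The cost is a few sentences. No protocol amendment is needed: Protocol 10.2.3 only permits the imputation, and Protocol 10.2.4 leaves analysis details to the SAP. The downside for the sponsor is that the reported robustness may look less favourable.

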## **5.9 Changes to Planned Analyses**

Any changes to the planned statistical analyses made prior to performing the primary endpoint analysis will be documented in an amended Statistical Analysis Plan approved prior to performing the analysis. Changes from the planned statistical methods after performing the analysis will be documented in the clinical study report along with a reason for the deviation.

# **6 VALIDATION**

All clinical data reports generated per this plan will be validated per [90702587](#), Global WI: Clinical Data Reporting Validation. The validation level R1 chosen for all primary, secondary, safety and other additional endpoints. The validation program includes checking logs and generating compare reports in comparing with main programming datasets. Statistical analyses and validation will be performed by IQVIA team.

# **7 PROGRAMMING CONSIDERATIONS**

All statistical programming tasks will be performed by IQVIA™ independently.

## **7.1 Statistical Software**

All statistical analyses will be done using The SAS System Version 9.4\_M6 software or above (Copyright© 2000 SAS Institute Inc., SAS Campus Drive, Cary, North Carolina 27513, USA. All rights reserved.).

## **7.2 Format of Output**

Results of analysis will be output programmatically to Microsoft Office® Word documents from SAS with no manual intervention. All output for the final statistical report will be in the form of a Word document containing tables, figures, graphs, and listings, as appropriate.

### 7.3 Methods for Handling Missing Data

Missing data will be excluded for primary analysis in this small sample size study.

Sensitivity Analysis will be performed by imputing missing values with Last Observation Carried Forward (LOCF) method and Worst-case scenario method using values at baseline where applicable for continuous variable.

When calculating rates of all adverse events, both device and/or procedure related with missing event date (i.e. mm/dd/yyyy), the ideal is to work with safety and/or data management representatives to query sites for missing data. However missing and partial missing dates may be handled as using the worst-case scenario as follows:

Partial Date	Action Taken
Entire adverse event onset date is missing	The procedure date will be used for the onset date.
The month and the day of the month are missing but the year is available	January 1 st will be used for the month and day of the onset date. However, if the imputed date falls before the procedure date, then the procedure date will be used for the onset date.
Day is missing, but the month and year are available	The 1 st will be used as the day of the onset date. However, if the imputed date falls before the procedure date, then the procedure date will be used for the onset date.

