7.3. Justification for the Study Design

The Rezūm System has got CE mark and FDA approval in 2013 and 2015 respectively, and a series of clinical studies have been conducted worldwide, such as FIM, Rezūm I, Rezūm II RCT, and demonstrated its safety and efficacy from histopathology and clinical medicine. Furthermore, it has been on the market for many years with consistently durable efficacy and mild AE. This retrospective study uses the data produced in hospitals in BOAO medical pilot zone, to evaluate its safety and performance in Chinese BPH patients, which will provide real world evidence for extensive use in China and approval as well.

8. Subject Selection

8.1. *Study Population and Eligibility*

Target populations are BPHs who were treated with Rezūm system in hospitals in Hainan medical pilot zone. To be eligible for enrollment in the study, subjects must meet all of the inclusion criteria.

8.2. *Inclusion Criteria*

Subjects who meet all inclusion criteria, and don't meet exclusion criteria will be eligible for enrollment.

- The subjects will provide written informed consent form and agree to data collection.
- The subjects who were diagnosed as BPH and treated by Rezūm procedure in Hainan medical pilot zone with complete procedure recorded.

8.3. *Exclusion Criteria*

This is a retrospective study without any formal exclusion criteria.

9. Study Methods

9.1. *Data Collection*

The data collection schedule is shown in Table 9.1-1.

Table 9.1-1: The data collection schedule

| Procedure/Assessment | Baseline/pre-procedure | Index Procedure | Post procedure/ Prehospital Discharge | follow-up post-procedure # |
|---|------------------------|-----------------|--|----------------------------|
| Informed consent | | | | X& |
| Demographics | X | | | |
| Medical history | X | | | |
| Physical examination (height, weight, etc) | X | | | X |
| Prostate volume (MRI, DUS)* | X | | | X |
| Uroflowmetry(Qmax, Urinary volume) | X | | | X |
| PVR | X | | | X |
| IPSS | X | | | X |
| QoL | X | | | X |
| IIEF | X | | | X |
| MSHQ-EjD | X | | | X |
| Procedure information | | X | | |
| Length of catheterization | | | X | |
| Surgical retreatment | | | | X |
| Medication(s) used(LUTS /BPH) | X | | X | X |
| Device Defect (if available) | | X | | |
| Adverse events assessment | | X | X | X |

Note: # All information of subjects available before the defined end of study will be collected in this retrospectively study, data missing will be allowed.

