9.4. Data collection: Baseline-procedure-discharge

The pre-procedure examination, procedure and information at discharge of the selected subjects will be collected from the electronic medical record database or paper medical records of hospitals in Hainan Boao Medical Pilot zone.

- Baseline/pre-procedure: Demographics, medical history, physical examination, prostate volume (MRI, DUS), PVR, Uroflowmetry(Qmax, Urinary volume), IPSS and quality of Life questionnaire, sexual function (IIEF and MSHQ-EjD , if available), Medication(s) used(LUTS /BPH).
- Procedure : anesthesia method, Rezūm operation time, key points of operation of Rezūm system, Device Defect (if available),adverse events, etc. Rezūm Operation time is from the time of insertion to the time the Rezūm Delivery Device removed.
- Discharge: Length of catheterization, Medication(s) used(LUTS /BPH), adverse events, etc. Length of Catheterization is from the time of insertion to time the catheter removed.

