16.1. Reportable Events by investigational site to Boston Scientific

It is the responsibility of the investigator to assess and report to BSC any event which occurs in any of following categories:

- All adverse events
- All Serious Adverse Events

- All device related adverse events
- All device related Serious Adverse Events
- All procedure related adverse events
- All procedure related Serious Adverse Events
- All Device Deficiencies
- Unanticipated Adverse Device Effects/Unanticipated Serious Adverse Device Effects
- New findings/updates in relation to already reported events

When possible, the medical diagnosis should be reported as the Event Term instead of individual symptoms.

If it is unclear whether or not an event fits one of the above categories, or if the event cannot be isolated from the device or procedure, it should be submitted as an adverse event and/or device deficiency.

Any reportable event, whether prior to, during or subsequent to the procedure, must be recorded in the CRF.

Underlying diseases and chronic conditions are not reported as AEs unless there is an increase in severity or frequency during the course of the investigation. Death should not be recorded as an AE, but should only be reflected as an outcome of one (1) specific SAE (see Table 16.2-1 for AE definitions).

Refer to Instructions for Use for the known risks associated with the commercial device(s).

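### The SAP's partial-date rule moves adverse events known to precede the procedure onto the procedure day, and the Protocol is inconsistent on whether such events are collected

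*SAP*

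**What the plan says.** **Which events are recorded.** Protocol 16.1 makes all adverse events and all serious adverse events reportable, gives no start date, and adds: "Any reportable event, whether prior to, during or subsequent to the procedure, must be recorded in the CRF". It limits this for pre-existing disease: "Underlying diseases and chronic conditions are not reported as AEs unless there is an increase in severity or frequency during the course of the investigation".

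**When collection starts.** The adverse-event row of Protocol Table 9.1-1, repeated in SAP section 2, has an empty baseline cell: "Adverse events assessment | | X | X | X". Protocol 9.4 agrees with the table. Its baseline list includes medical history but no adverse events, which appear only under procedure and discharge.

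**How missing dates are handled.** SAP 7.3 prefers that sites be queried, and then offers a fallback: "However missing and partial missing dates may be handled as using the worst-case scenario as follows". For a wholly missing date, "The procedure date will be used for the onset date". If only the year is known, the onset becomes 1 January of that year. If month and year are known, it becomes the first of that month. Both partial-date rows end with the same condition: "However, if the imputed date falls before the procedure date, then the procedure date will be used for the onset date".

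**Where the dates could matter.** The primary safety window runs from the procedure (Protocol 6.2.1.2) to day 182 (SAP 3.2). All SAEs is a secondary endpoint (Protocol 6.2.2, SAP 5.1). SAP 5.8 tabulates non-serious and serious events by system organ class and preferred term. The SAP defines no treatment-emergent event and does not split events at the procedure.

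**The concern.** A worst-case date rule should resolve uncertainty against the device. When an event is recorded only in the month, or only in the year, of the procedure, its order relative to treatment is unknown, and placing it on the procedure day is ordinary caution. When the recorded month or year is already earlier, the order is known. The rule then overwrites recorded information and gives a pre-treatment event a day-0 onset.

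This could be dismissed if pre-procedure events never entered the adverse-event data, but Protocol 16.1 says they must be recorded, against the schedule and Protocol 9.4. At stake is whether the All SAEs result and the adverse-event tables describe what happened after treatment. With at most 30 subjects, one event is visible in any rate.

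**Working it through.** The documents state no figure on this point, so the check is one of logic, followed by the weight of a single event.

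**1. The rule.** Let P be the procedure date, T the true onset, and D the imputed date (first of the known month, or 1 January of the known year). SAP 7.3 sets onset = P if D < P, and onset = D otherwise. D is the earliest day compatible with the recorded part, so D ≤ T. If the event preceded the procedure, T < P, hence D ≤ T < P and the onset is always P. No partly dated pre-procedure event can stay pre-procedure.

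**2. Illustrations (assumed dates).**
- Recorded as March 2021, procedure 10 May 2021: D = 1 March 2021, which is before P, so onset = 10 May 2021.
- Recorded as 2020, procedure in 2021: D = 1 January 2020, which is before P, so onset = the procedure date.

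In both, the record alone shows that the event came first.

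**3. How often the record settles the order.** The rule was applied to all 365 procedure dates in an assumed year (2021), each with every true onset 1 to 365 days earlier: 365 × 365 = 133,225 cases for each type of partial date. All were moved to the procedure day.

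| Recorded part | Known to be earlier | Ambiguous (same month, or same year) |
|---|---|---|
| Month and year | 127,852 (96%) | 5,373 (4%) |
| Year only | 66,795 (50%) | 66,430 (50%) |

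The middle column is what a corrected rule would leave before the procedure. The shares depend on the assumed uniform one-year look-back and do not predict this study's data.

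**4. Effect on each output.**
- *Primary safety composite.* It needs a device perforation, a device-related fistula, or de novo severe retention lasting more than 21 consecutive days post treatment. A pre-treatment episode fails these definitions whatever onset date is imputed.
- *All SAEs and the tables by system organ class and preferred term.* No date filter is stated. If none is applied, a fully dated pre-procedure event is counted just as a partly dated one is, and the imputation changes only the recorded day. If programmers restrict the tables to onset on or after the procedure, fully dated earlier events drop out and partly dated ones stay in. Either way the tables mix pre- and post-treatment events, so the date rule and the missing definition have to be settled together.

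**5. Weight of one event.** The safety set is all enrolled treated subjects (SAP 4.1.2), planned at up to 30. Exact (Clopper-Pearson) two-sided 95% limits are:
- 0/30 = 0%, upper limit 11.6%.
- 1/30 = 3.3%, limits 0.1% to 17.2%.

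If the safety set were as small as 22 (the target number with valid data, used here as a lower extreme), 1/22 = 4.5% and the upper limit would go from 15.4% at 0/22 to 22.8% at 1/22.

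**The case against.** The strongest reply is that the rule changes little in practice. Five parts of it deserve an answer.

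- *The rule is a fallback.* Sites are queried first and the wording is permissive. That stands, and it lowers the expected number of affected events. But no other fallback is written, and optional wording leaves the choice open at analysis.
- *Any error counts against the device.* True, but worst-case handling is a way to treat uncertainty. It gives no reason to override a date part that already fixes the order.
- *Pre-treatment conditions are mostly medical history.* Largely so. Protocol 16.1 excludes underlying and chronic conditions unless they worsen, and long-standing retention from BPH would usually fall there. Acute earlier events such as an infection are not excluded. The exclusion also refers to the course of the investigation, whose start is not defined in a study where consent follows treatment.
- *The scope may be narrower.* SAP 7.3 introduces the rule for all adverse events and then mentions device and/or procedure relationship. If only related events are meant, most pre-procedure events fall outside it. The documents do not settle this.
- *No decision depends on it.* Correct: there is no safety hypothesis or performance goal.

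A reader might infer that the rule inflates the primary safety endpoint. The documents do not support that, because the component definitions and the investigator's assessment of device relationship screen out pre-treatment events. A reader might also infer that the imputation alone brings pre-treatment events into the adverse-event rates. That is also too strong: with no date filter in SAP 5.8, fully dated earlier events could be counted too.

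**Conclusion.** The point holds as a limited defect. As written, SAP 7.3 gives a day-0 onset to every partly dated event that preceded the procedure, including those whose recorded month or year proves it. The Protocol is inconsistent on whether such events belong in the adverse-event data at all. The exposure is the All SAEs endpoint and the adverse-event tables, at about 3.3 percentage points per affected subject with 30 in the safety set.

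The number of affected subjects is unknown and probably small. Each would need an earlier event entered as an adverse event rather than as history, partly dated, unresolved by query, and within the scope of the rule. The documents give no basis for estimating how common partial dates will be. The change is worth making because the rule contradicts known information and is easy to correct; no primary conclusion depends on it.

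**What to change.** 1. In SAP 7.3, reset a partial date to the procedure date only when the known month and year, or the year if only that is known, equals that of the procedure. Keep the present handling of wholly missing dates. State whether the rule covers all adverse events or only related ones.
2. State in the SAP that any event known to have started before the procedure, fully or partly dated, is listed separately and left out of the post-procedure adverse-event and serious-adverse-event rates. Without this, the first change would treat partly dated events differently from fully dated ones.
3. Reconcile Protocol 16.1 with Table 9.1-1 and Protocol 9.4 on when adverse-event collection starts and where earlier events are recorded.

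The cost is one condition in the date program, a short definition, a Protocol wording change with its ethics committee review, and one extra short listing. No new data are needed. SAP 5.9 already provides for an amended plan approved before the primary endpoint analysis.
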